		cerebrovascular disease I 169.991, Dysphagia following unspecified cerebrovascular disease Amyotrophic lateral sclerosis: ICD-10-CM codes: G12.20, Motor neuron disease, unspecified G12.21, Amyotrophic lateral sclerosis Muscular dystrophy: ICD-10-CM codes: G71.0, Muscular dystrophy Other neurological disease: R41, R41.x, R41.xx, Other symptoms and signs involving cognitive functions and awareness R42, Dizziness and giddiness R43, R43.x, Disturbances of smell and taste

Variable	Description	Operational definition
v arrabic	Description	 R44, R44.x, Other symptoms and signs involving general sensations and perceptions R45, R45.x, R45.xx, Symptoms and signs involving emotional state R46, R46.x, R46.xx, Symptoms and signs involving appearance and behavior Respiratory Asthma: ICD-10-CM codes: J45.2x–J45.3x, Mild intermittent asthma J45.4x, Moderate persistent asthma
		 J45.5x, Severe persistent asthma J45.9x, Other and unspecified asthma
		Chronic bronchiectasis: ICD-10-CM codes:
		J47.0, J47.1, J47.9, Bronchiectasis COPD/interstitial lung disease/ emphysema:
		■ ICD-10-CM codes:

Variable	Description	Operational definition
		■ J41.x Simple and mucopurulent chronic bronchitis ■ J42, Unspecified chronic bronchitis ■ J43.x, Emphysema ■ J44.x, Other COPD ■ J80, J81.x, J82.xx, J84.xx, J84.xxx, Other respiratory diseases principally affecting the interstitium ■ M05.10, Rheumatoid lung disease with rheumatoid arthritis of unspecified site Cystic fibrosis: ■ ICD-10-CM codes: ■ E84.x, E84.xx, Cystic fibrosis Obstructive sleep apnea: ■ ICD-10-CM codes: ■ G47.33 Obstructive sleep apnea (adult) (pediatric) Pneumonia: ■ ICD-10-CM codes: ■ J12.x, J12.xx Viral pneumonia, not elsewhere classified ■ J13 Pneumonia due to Streptococcus pneumoniae

Variable	Description	Operational definition
		■ J14 Pneumonia due to Hemophilus influenzae ■ J15.x, J15.xxx Bacterial pneumonia, not elsewhere classified ■ J16.x Pneumonia due to other infectious organisms, not elsewhere classified ■ J17 Pneumonia in diseases classified elsewhere ■ J18.x Pneumonia, unspecified organism Other Cancer: ■ ICD-10-CM codes: ■ C00-C75, C00.x-C75.x, C00.xx-C75.xx, C7A., C7A.x, C7A.xx, C7B., C7B.x, C7B.xx, Malignant neoplasms, stated or presumed to be primary (of specified sites), and certain specified histologies, except neuroendocrine, and of lymphoid, hematopoietic and related tissue ■ C76-C80, C76.x-C80.x, C76.xx-C80.xx, Malignant neoplasms of ill-defined,

Variable	Description	Operational definition
		other secondary and unspecified sites C81—C96, C81.x—C96.x, C81.xx—C96.x, C81.xx—C96.xx, Malignant neoplasms of lymphoid, hematopoietic and related tissue Chronic kidney disease/dialysis: ICD-10-CM codes: D59.3, Hemolytic-uremic syndrome 112.x, Hypertensive chronic kidney disease 113.x, I13.xx, Hypertensive heart and chronic kidney disease 170.1, Atherosclerosis of renal artery 172.2 Aneurysm of renal artery K76.7, Hepatorenal syndrome M10.30—M10.39, M10.37x, Gout due to renal impairment M32.14, Glomerular disease in systemic lupus erythematosus

Variable	Description	Operational definition
		 M32.15, Tubulo-interstitial nephropathy in systemic lupus erythematosus M35.04, Sicca syndrome with tubulo-interstitial nephropathy N00.x-N07.x, N08, Glomerular diseases N13.1, N13.2, N13.3x, Obstructive and reflux uropathy N14.x, Nephropathy N15.x, Other renal tubulo-interstitial diseases N16, Renal tubulo-interstitial disorders in diseases classified elsewhere N17.x, N18.x, N19, Acute kidney failure and chronic kidney disease N25.x, N26.x, N25.xx, Other disorders of kidney and ureter Q61.02, Q61.11x, Q61.2-Q61.9, Cystic kidney disease Q62.x, Q62.xx, Congenital obstructive defects of renal

Variable	Description	Operational definition
		pelvis and congenital malformation of ureter Diabetes mellitus without complications: ICD-10-CM codes: E10.9, Type 1 diabetes mellitus without complications E11.9, Type 2 diabetes mellitus without complications Diabetes mellitus with complications: ICD-10-CM codes: E10.x (excluding E10.9), E10.xx, E10.xxx, Type 1 diabetes mellitus with complications E11.x (excluding E11.9), E11.xx, E11.xxx, Type 2 diabetes mellitus with complications Down syndrome:
		ICD-10-CM codes:Q90.x, Down syndrome
		End stage renal disease: ICD-10-CM codes: N18.6, End stage renal disease I12.0, Hypertensive chronic kidney disease with stage 5 chronic kidney

Description	Operational definition
	disease or end stage renal disease Il 3.1, Hypertensive heart and chronic kidney disease without heart failure Il 3.2, Hypertensive heart and chronic kidney disease with heart failure and with stage 5 chronic kidney disease, or end stage renal disease Gout: ICD-10-CM codes: M10.00, M1A.9XX0, M1A.00X1, M1A.20X1, M1A.30X1, M1A.40X1, M1A.9XX1, M10.30, N20.0, M10.9, M10.40, M11.80, M11.819, M11.829, M11.839, M11.849, M11.859, M11.849, M11.859, M11.869, M11.879, M11.88, M11.89, M11.20, M11.219, M11.229, M11.239, M11.249, M11.259, M11.269, M11.279, M11.28, M11.29, M11.
	Description

Variable	Description	Operational definition
		Hyperlipidemia F18.0–E78.5, E78.0x, E78.4x, Hyperlipidemia Hyperthyroidism (excluding autoimmune thyroiditis): F105-10-CM codes: F105.x, E05.xx, Hyperthyroidism Illicit drug use: F11.xx, F11.xxx, Opioid related disorders F12.xx, F12.xxx, Cannabis related disorders F14.xx, F14.xxx, Cocaine related disorders F16.xx, F16.xxx, Hallucinogen related disorders F18.xx, F18.xxx, Inhalent related disorders F19.xx, F19.xxx, Other psychoactive substance related disorders F19.xx, F19.xxx, Other psychoactive substance related disorders T72.51, For counseling/surveillance of the drug abuser Stimulant use: F10-10-CM codes:

Variable	Description	Operational definition
		 F14.xx, F14,xxx, Cocaine related disorders F15.xx, F15.xxx, Other stimulant related disorders Metabolic syndrome ICD-10-CM codes: E88.810, Metabolic syndrome Panic disorders ICD-10-CM codes: F40.01, Agoraphobia with panic disorder [episodic paroxysmal anxiety] Reaction to stress ICD-10-CM codes: F43.0, Acute stress reaction F43.1x, Post-traumatic stress disorder F43.8x, Other reactions to severe stress F43.9, Reaction to severe stress, unspecified
Concomitant medications	Categorical variable: • Antineoplastic (ie, 7-con-o-methylnogaril, aclacinomycin a, cisplatin, doxorubicin,	Medications will be identified by string searching the specific medication names and using NDC codes that will be described in the SAP.

Variable	Description	Operational definition
	etaracizumab, ifosfamide, melphalan, mitoxantrone, trastuzumab) • Bisphosphonates (ie, alendronate) • Cardiovascular (ie, adenosine, dobutamine) • Central nervous system (ie, clozapine, morphine) ie	
Other medications/procedures (identified outside of the AHA criteria)	 NSAIDs Respiratory (ie, theophylline) Ivabradine Digitalis CAR T-cell therapy*\$ 	Other medications/procedures will be identified by string searching the specific medication or procedure names and using NDC codes or HCPCS codes, CPT codes, and ICD-10-CM codes that will be described in the SAP. CAR T-cell therapy: CPT codes: 0537T, 0538T, 0539T, 0540T ICD-10-PCS codes: XW033C3, XW043C3, Q2041, Q2042
History of immunization	Categorical variable: • Seasonal influenza • COVID-19 • Tetanus diphtheria and pertussis (Tdap or Td) • Chickenpox (Varicella) • Shingles (Herpes Zoster recombinant and/or live)	See Annex 3 Table A-3 for vaccine codes

PFIZER CONFIDENTIAL

Variable	Description	Operational definition
	 HPV Pneumococcal conjugate Pneumococcal polysaccharide Hepatitis A Hepatitis B MenACWY and MenB Haemophilus influenzae type b 	
Co-administered immunizations (same list as history of immunizations)	 Seasonal influenza vaccine COVID-19 Tetanus diphtheria and pertussis (Tdap or Td) Chickenpox (varicella) Shingles (herpes zoster recombinant and/or live) HPV Pneumococcal conjugate Pneumococcal polysaccharide Hepatitis A Hepatitis B MenACWY and MenB Haemophilus influenzae type b 	See Annex 3 Table A-3 for vaccine codes

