 - Individuals in the unvaccinated control cohort who go on to receive an RSV vaccine following their index date will be censored at the time of RSV vaccination. If the RSV vaccine is ABRYSVO, these individuals will contribute to the ABRYSVO cohort starting from the date of ABRYSVO receipt.
- o Regular use of preventive medical care, defined as at least one vaccination record between 365 to 31 days prior to the index date.

In addition, individuals in all cohorts must meet the following inclusion criteria to be eligible for the study:

- At least 2 years of continuous enrollment in (ie, no disenrollment from) VHA benefits (ie, the baseline period) prior to the index date
- Complete follow-up (ie, no disenrollment from VHA benefits, death, or receipt of RSV vaccination [for controls who may later receive any RSV vaccine only]) during the risk interval and confirmatory diagnosis window (eg, 34 days of complete follow-up for 0-3 days primary risk interval plus 30-day confirmatory diagnosis window; or 32 days or 61 days for secondary analysis with 0-1 days and 0-30 days risk intervals plus 30-day confirmatory diagnosis window, respectively).

Based on age on the index date, eligible individuals will be further classified into the following two age groups with the following additional inclusion criteria:

- 18-59 years old age group
 - o 18-59 years of age on the index date
 - o For individuals in cohorts B and C, a record for specific conditions that increase the risk for severe RSV as defined by the CDC during the baseline period, identified as those with chronic cardiovascular disease, chronic lung or respiratory disease, end-stage renal disease or dependence on hemodialysis or other renal replacement therapy, diabetes mellitus with complications, neurologic or neuromuscular conditions causing impaired airway clearance or respiratory muscle weakness, chronic liver disease, chronic hematologic

conditions, severe obesity, moderate or severe immune compromise, residence in a nursing home, or other chronic medical conditions or risk factors that a health care provider determines would increase the risk for severe disease due to viral respiratory infection (eg, frailty); list of conditions may be updated to align with the most current CDC definition at the time of data analysis¹⁹

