- Moderate and severe immunocompromising conditions will include solid tumor and hematologic malignancies, receipt of solid-organ transplant or an islet transplant, receipt of chimeric antigen receptor (CAR) T-cell therapy or hematopoietic cell transplant (HCT) (within 2 years of transplantation), moderate or severe primary immunodeficiency, and human immunodeficiency virus [HIV] infection)¹⁹
- 60 years and older age group
 - o At least 60 years of age on the index date

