	 Cystic fibrosis*§ Obstructive sleep apnea Pneumonia Other Cancer Chronic kidney disease/dialysis§ Diabetes mellitus without complications Diabetes mellitus with complications*§ Down syndrome End-stage renal disease*§ Gout Hyperlipidemia Hyperlipidemia Hyperthyroidism (excluding autoimmune thyroiditis) Illicit drug use (eg, cocaine) Metabolic syndrome Panic disorders Stimulant use (eg, amphetamines, caffeine) Severe obesity (BMI ≥40 kg/m²)§ Reaction to stress * ICD-10-CM diagnosis codes, ICD-10-PCS codes, CPT, or HCPCS procedure codes will be provided in the SAP. § Conditions that increase the risk of RSV as defined according to CDC.¹9 	■ ICD-10-CM codes: ■ I40.x, Acute myocarditis ■ I41, Myocarditis in diseases classified elsewhere ■ I51.4, Myocarditis, unspecified ■ B33.22, Viral myocarditis Pericarditis: ■ ICD-10-CM codes: ■ I30.x, Acute pericarditis ■ I32, Pericarditis in diseases classified elsewhere ■ B33.23, Viral pericarditis Stroke/transient ischemic attack: ■ ICD-10-CM codes: ■ G43.601, G43.609, G43.611, G43.619, I60.9, I62.00, I61.9, I62.1, I62.9, I63.019, I63.119, I63.139, I63.20, I63.219, I63.22, I63.239, I63.219, I63.22, I63.239, I63.30, I63.40, I63.50, I63.59, I66.09, I66.19, I66.29, I66.9, I67.89, I69.898, I69.90, I69.910, I69.911, I69.912, I69.913, I69.914, I69.915, I69.913, I69.914, I69.915, I69.918, I69.919, I69.920, I69.921, I69.922, I69.923, I69.928, I69.941, I69.942,

Variable	Description	Operational definition
		I69.943, I69.944, I69.949, I69.951, I69.951, I69.952, I69.953, I69.954, I69.959, I69.961, I69.962, I69.963, I69.964, I69.965, I69.969, I69.990, I69.991, I69.992, I69.993, I69.998, Stroke G45, Transient ischemic attack Hematological Bleeding diathesis or condition associated with prolonged bleeding: ICD-10-CM codes: D65, Disseminated intravascular coagulation D66, Hereditary factor VIII deficiency D67, Hereditary factor IX deficiency D68, D68.x, D68.xx, Other coagulation defects D69, D69.x, D69.xx, Purpura and other hemorrhagic conditions Hematologic malignancy: ICD-10-CM codes: C81, C82, C83, C88, C89, C90, C91, C92, C93, C94, C95, C96, Hematologic malignancy

Variable	Description	Operational definition
		Sickle cell disease: ICD-10-CM codes: D57, D57.x, D57.xx, D57.xxx, Sickle-cell disorders
		Thalassemia: ICD-10-CM codes: D56.x, Thalassemia VTE:

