Vaccine	Code Type	Code	Manufacturer/Description
	Турс		
	CPT	90650	HPV vaccine, types 16, 18, bivalent
			(2vHPV), 3 dose schedule, for
			intramuscular use
	CPT	90651	HPV vaccine types 6, 11, 16, 18,
			31, 33, 45, 52, 58, nonavalent
			(9vHPV), 2 or 3 dose schedule, for
			intramuscular use
Pneumococcal	CPT	90669	Pneumococcal conjugate vaccine, 7
conjugate		225	valent, for intramuscular use
	CPT	90670	Pneumococcal conjugate vaccine,
			13 valent (PCV13), for
	HCPCS	G0009	intramuscular use
	ncres	G0009	Administration of pneumococcal vaccine
	HCPCS	G8864	Code for Pneumococcal vaccine
	licies	G0004	administered or previously received
Pneumococcal	CPT	90732	Pneumococcal polysaccharide
polysaccharide		70732	vaccine, 23-valent (PPSV23), adult
r - J - m - m - m -			or immunosuppressed patient
			dosage, when administered to
			individuals 2 years or older, for
			subcutaneous or intramuscular use
Hepatitis A	CPT	90632	Hepatitis A vaccine, adult dosage,
			for intramuscular use
	CPT	90633	Hepatitis A vaccine (HepA),
			pediatric/adolescent dosage-2 dose
	CDT	00624	schedule, for intramuscular use
	CPT	90634	Hepatitis A vaccine (HepA),
			pediatric/adolescent dosage-3 dose
	СРТ	90730	schedule, for intramuscular use
			Hepatitis A vaccine
	CPT	90636	Hepatitis A and hepatitis B vaccine
			(HepA-HepB), adult dosage, for intramuscular use
Hepatitis B	CPT	90371	Hepatitis B immune globulin
перания в		703/1	(HBIg), human, for intramuscular
			use
	CPT	90739	Hepatitis B vaccine (HepB), adult
			dosage, 2 dose schedule, for
			intramuscular use
	CPT	90740	Hepatitis B vaccine (HepB), dialysis
			or immunosuppressed patient

Vaccine	Code Type	Code	Manufacturer/Description
			dosage, 3 dose schedule, for intramuscular use
	CPT	90743	Hepatitis B vaccine (HepB), adolescent, 2 dose schedule, for intramuscular use
	CPT	90744	Hepatitis B vaccine (HepB), pediatric/adolescent dosage, 3 dose schedule, for intramuscular use
	CPT	90745	Hepatitis B vaccine, adolescent/high risk infant dosage, for intramuscular use
	CPT	90746	Hepatitis B vaccine (HepB), adult dosage, 3 dose schedule, for intramuscular use
	CPT	90747	Hepatitis B vaccine (HepB), dialysis or immunosuppressed patient dosage, 4 dose schedule, for intramuscular use
	HCPCS	G0010	Administration of Hepatitis B vaccine
MenACWY and MenB	CPT	90619	MenACWY, serogroups A, C, W, Y, quadrivalent, tetanus toxoid carrier (MenACWY-TT), for intramuscular use

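### Annex code lists for the CDC risk conditions and the comparator vaccines do not match the written criteria, and can both admit ineligible and exclude eligible people

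*Protocol*

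**What the plan says.** **Risk condition, ages 18-59.** Protocol Section 9.2.1 sets this rule, with the two-year baseline as the look-back: "For individuals in cohorts B and C, a record for specific conditions that increase the risk for severe RSV as defined by the CDC". ABRYSVO recipients of the same age need no such record. On malignancy the section says "Moderate and severe immunocompromising conditions will include solid tumor and hematologic malignancies". On kidney disease it names "end-stage renal disease or dependence on hemodialysis or other renal replacement therapy". The list of conditions closes with a catch-all: "other chronic medical conditions or risk factors that a health care provider determines would increase the risk for severe disease". The same conditions define a subgroup of those aged 60 and over (Section 9.2.3).

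**Codes for those conditions.** Section 9.3.3 and Annex 3 Table A-2 mark CDC risk conditions with §. Table A-2 codes the separate hematologic malignancy item as "C81, C82, C83, C88, C89, C90, C91, C92, C93, C94, C95, C96, Hematologic malignancy". The combined hematologic-or-solid-malignancy item repeats that list and adds a solid list. The § item for chronic kidney disease/dialysis includes "N17.x, N18.x, N19, Acute kidney failure and chronic kidney disease".

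**Comparator vaccines.** Cohort B in Section 9.2.1 is built from vaccines listed in Section 9.3.3, and the control's index date is the date of that vaccine. Section 9.3.3 refers to Annex 3 Table A-3 for codes. That table carries CPT 90396 (varicella-zoster immune globulin) under both chickenpox and shingles, CPT 90371 (hepatitis B immune globulin) under hepatitis B, and HCPCS G8864 under pneumococcal conjugate, described as vaccine "administered or previously received".

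**The concern.** The risk-condition rule filters only the comparator cohorts in the younger age group, so the codes that implement it help decide who can be a control. If a list is too wide, people without a listed condition enter the pool. If it is too narrow, people who meet the written criterion are left out. The malignancy list does both.

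For the vaccine codes the stake is timing. The primary risk interval is days 0-3, four days in all. If a record of immune globulin, or of a vaccine received earlier, sets day 0, the whole window for that control is anchored to a day on which no vaccine was given. The same codes can disturb the tests for unvaccinated controls in Section 9.2.1: no other vaccine on or within 30 days of the index date, and at least one vaccination record 365 to 31 days before it.

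**Working it through.** No power or sample-size figure is involved. The check compares the printed lists with each other and with the written criteria.

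1. **Hematologic list against the Cancer row.** Table A-2's Cancer item uses C81-C96 unbroken, labelled "Malignant neoplasms of lymphoid, hematopoietic and related tissue". That range has 96 - 81 + 1 = 16 categories. The hematologic list has 12 (C81-C83 and C88-C96). The numerical gap is C84, C85, C86 and C87; nothing here turns on C87. The gap appears in both the separate and the combined item.

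2. **Solid list against the Cancer row.** C00-C80 has 81 two-digit categories. The solid list has C00-C07 (8), C11-C19 (9) and C22-C80 (59), which makes 76. The missing five are C08, C09, C10, C20 and C21.

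3. **Entries outside the Cancer row.** The Cancer row contains C00-C96, C7A and C7B. The solid list adds Z85, D3A and D00-D49: 1 + 1 + 50 = 52 entries. The Charlson malignancy component in the same table also covers C81-C96, says that it includes lymphoma and leukemia, and has no D codes and no Z85. Two of the annex's own definitions therefore disagree with the § item. The Cancer item has no § mark, so it does not bring back people whose only code is an omitted one.

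4. **Kidney.** Section 9.2.1 names end-stage disease or renal replacement therapy. The § item for chronic kidney disease/dialysis covers N17.x (acute failure), all of N18.x, N19, and glomerular, obstructive and congenital codes. A separate § item for end-stage renal disease exists, but it lists I13.1, whose printed label does not mention end-stage disease.

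5. **Vaccines.** The chain from cohort B to Section 9.3.3 to Table A-3 is explicit. By their printed labels, 90396 and 90371 are immune globulins. G8864 does not separate a dose given that day from an earlier one.

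6. **Who is reached.** Points 1-4 concern controls aged 18-59 and the 60+ risk-condition subgroup. Point 5 concerns vaccinated controls of any age and the vaccination-record tests for unvaccinated controls.

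**The case against.** - **The link from Table A-2 to eligibility is inferred.** Section 9.2.1 defines the conditions in words and cites no annex. Table A-2 is presented as baseline characteristics, and in Section 9.3.3 the combined malignancy item itself lacks the § mark, although its parent heading has it. This stands, and it is why the point says *appear to operationalise*. Table A-2 is nonetheless the only coding of these conditions in the protocol.
- **The SAP may revise the codes.** Section 9.3.3 allows annex codes to be updated where needed. However, Table A-2 puts an asterisk on items whose codes the SAP will supply, end-stage renal disease among them. The malignancy and chronic kidney disease/dialysis items have no asterisk, so their codes are stated rather than deferred.
- **The catch-all could cover non-end-stage kidney disease.** It could cover some chronic disease. It speaks of chronic conditions, so it does not reach acute kidney failure.
- **An immune globulin is not a vaccine, so the written rule for cohort B already excludes it.** In words, yes. A program that follows Table A-3 would still count it.
- **ATT weighting will absorb this.** It may reduce imbalance on measured covariates, and the Cancer item is available as one. It cannot restore excluded controls or correct an index date.
- **The reach is limited.** The main 60+ comparison needs no risk condition. The 18-59 comparison runs only with enough events: an IRR of 2.0 needs 286,730 vaccinees, against 330,000 to 868,000 possibly eligible enrollees, that is 286,730/868,000 = 33% to 286,730/330,000 = 87% of them. This stands.

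A reader might infer that a large share of the younger control pool would be healthy people with a benign-lesion code. The documents do not support that. The annex prints no labels for D00-D49 or Z85, and nothing gives the share of enrollees whose only qualifying code is one of these.

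**Conclusion.** The mismatch is real and can be shown from the protocol alone. The § malignancy coding omits C84-C86, C08-C10 and C20-C21 and adds 52 entries that the annex's own Cancer row does not contain. The § kidney coding goes beyond the written criterion, with acute kidney failure as the clear case. Table A-3 treats three codes as vaccinations that need not mark a vaccine given on that day.

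The effect runs both ways: ineligible people can be admitted and eligible people excluded. Neither its size nor the direction of any bias in the hazard ratio can be derived from the protocol. It would be wrong to read this as undermining the main 60+ comparison, which the risk-condition codes do not touch; only the vaccine codes reach it.

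The conclusion on Table A-2 assumes that the § items will be used to apply Section 9.2.1. The conclusion on Table A-3 rests on an explicit reference. The point merits correction as a matter of consistency. It is not a reason to doubt the design.

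**What to change.** 1. Use one malignancy definition for the § items, matching the C-code ranges of the Cancer row in Table A-2.
2. Reconcile the § kidney items with Section 9.2.1 so that one definition governs eligibility, either by restricting the codes or by widening the written criterion. Settle acute kidney failure and I13.1 in the same step.
3. Remove 90371, 90396 and G8864 from the codes that define a vaccination or an index date.
4. State in Section 9.2.1 which code list determines eligibility.

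The cost is a set of code-list edits and one sentence, plus some change in the size of the 18-59 control pool: dropping entries shrinks it, and adding the omitted C codes enlarges it. The edits are cheapest before data extraction (planned start 24 February 2025). If extraction has already run, cohort selection would have to be repeated with the corrected lists.
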